## 12. CONCURRENT DISEASE

Concurrent Disease will be presented for the SAF population.

- Concurrent Diseases will be coded using Medical Dictionary for Regulatory Activities (MedDRA, Version 26.0 or latest) dictionary
  - Concurrent Diseases are conditions started prior to or at Screening and are ongoing at the date of Screening.
  - o Presented by SOC and PT.

Concurrent Diseases conditions are defined as those conditions recorded in the eCRF form "Medical History/Concurrent Diseases"

Page 25 of 46

## 13. PRIOR AND CONCOMITANT MEDICATIONS

Medications, recorded in the eCRF form "Prior and Concomitant Medications", will be presented for the SAF population and coded using WHO Drug dictionary Version 01SEP2022 or latest. Frequency tabulations will be presented for prior and concomitant medications by primary therapeutic subgroup (3rd level ATC code) and preferred name for Monotherapy and Combination Therapy.

See APPENDIX 2 for handling of partial dates for medications, in the case where it is not possible to define a medication as prior, concomitant, or post treatment, the medication will be classified by the worst case, i.e., concomitant.

- 'Prior' medications are medications which started and stopped prior to the first dose of monotherapy.
- 'Concomitant' medications are medications which:
  - o started prior to, on or after the first dose of study medication,
  - o AND ended on or after the date of first dose of study medication or were ongoing at the end of the study.
  - Concomitant medications that are started prior to the first dose of Combination Therapy will be summarized under "Monotherapy".

Concomitant medications that are started after the first dose of Combination Therapy will be summarized under "Combination Therapy"

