• To evaluate the safety and tolerability of the monotherapies (NEB 5 mg and RAM 5 mg) and of the extemporaneous combinations (NEB/RAM 5/2.5 mg, NEB/RAM 5/5 mg, NEB/RAM 5/10 mg).	 Safety and tolerability of the monotherapies (NEB 5 mg and RAM 5 mg) and of the extemporaneous combination (NEB/RAM 5/2.5 mg, NEB/RAM 5/10 mg) measured by incidence, intensity (severity), seriousness of Adverse Events (AEs) during the study period, (screening, Run-in period and Assessment period), relationship to the study treatments, clinically significant abnormal change in vital signs, electrocardiogram (ECG), laboratory parameters and use of concomitant medications at Visit 2 (Week 0), Visit 3 (Week 4), Visit 4 (Week 8) and Visit 5 (Week 12). 	• Incidence of adverse drug reactions (ADRs), AEs, serious adverse events (SAEs), needs to be studied to address safety and tolerability of the extemporaneous combination.
Exploratory		
• To assess the antihypertensive efficacy of the extemporaneous combination of NEB 5 mg with RAM 2.5/5/10 mg by evaluating the patients who achieved the standard BP goal (sitting BP < 140/90 mmHg) at Visit 2 (Week 0), at Visit 3 (Week 4) and at Visit 4 (Week 8).	• Number and proportion of patients achieving the standard BP goal (sitting BP < 140/90 mmHg) at Visit 2 (Week 0), Visit 3 (Week 4) and Visit 4 (Week 8).	• The proportion of patients achieving the target is a very important clinical indicator of therapeutic success. ¹⁹
• To assess the antihypertensive efficacy of the extemporaneous combination of NEB 5 mg with RAM 2.5/5/10 mg by evaluating the patients who achieved the optimal BP goal (sitting BP < 130/80 mmHg in patients < 65 years	 Number and proportion of patients achieving the optimal BP goal (sitting BP < 130/80 mmHg in patients < 65 years old/sitting BP < 140/80 mmHg in patients ≥ 65 years old) at Visit 2 (Week 0), Visit 3 (Week 4), and Visit 4 (Week 8). 	• The proportion of patients achieving the target is a very important clinical indicator of therapeutic success. ¹⁹

MENARIN	Global Medical Department		
	Protocol Template		
Identification Number	Version Number State Effective date		
FORM-000050125	3.0, CURRENT	Effective	13 May, 2022

OBJECTIVES	ENDPOINTS	JUSTIFICATION FOR ENDPOINTS
old/sitting BP < 140/80 mmHg in patients ≥ 65 years old) at Visit 2 (Week 0), at Visit 3 (Week 4), and at Visit 4 (Week 8).		

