7.5 Concomitant Therapy(ies)

Any medication that the patient was receiving at the time of enrolment and any other regular or occasional use of any concomitant medication during the study will be recorded in the source documents and in the eCRF. Whenever possible, without jeopardizing the patients care, study patients should remain on the same concomitant medication at a stable dose throughout the study. In order to facilitate recording of medication history, patients will be asked to bring their medication, preferably in their original packaging.

RENARIN	Global Medical Department		
	Protocol Template		
Identification Number	Version Number	State	Effective date
FORM-000050125	3.0, CURRENT	Effective	13 May, 2022

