12.5 Statistical Analysis

Descriptive statistics

Patient disposition, demographics and baseline characteristics will be summarized for monotherapy and combination therapy. Medical history will be summarized only for monotherapy. Prior and concomitant medications will be summarized for combination therapy (NEB + RAM).

Continuous variables will be summarized using the number of non-missing observations, mean, SD, minimum, median, and maximum values. Categorical variables will be presented with the number of non-missing observations and column percentages (n, %).

Primary (efficacy) analysis

The primary efficacy analysis will be conducted on the mITT population. The results will be interpreted for the same population.

The primary endpoint is the change in mean sitting SBP between Visit 2 (Week 0) and Visit 5 (Week 12).

The statistical hypothesis will be defined as below:

H0: There is no change in the sitting SBP post combination therapy.

H1: There is a difference in the sitting SBP post combination therapy.

The above hypothesis will be tested as following:

- Change from baseline in sitting SBP from prior and post combination therapy will be tested using paired t-test. The p-value obtained from the paired t-test will be presented.
- Assumption of Normality will be investigated using Wilk-Shapiro test. If the data is found to be non-Normal, the paired t-test will be replaced by Wilcoxon signed rank test.
- The primary endpoint will be summarized descriptively using n, mean, median, SD, Q1 (first quartile), Q3 (third quartile), minimum, and maximum.

MENARIN	Global Medical Department		
	Protocol Template		
Identification Number	Version Number	State	Effective date
FORM-000050125	3.0, CURRENT	Effective	13 May, 2022

Sensitivity analysis

The sensitivity analyses will be conducted using the PP population.

The PP population will be used to assess the robustness of the results obtained using the mITT population.

Secondary (efficacy) analysis

Secondary efficacy variables will be summarized in a descriptive manner using the mITT population.

- Change in mean sitting DBP between Visit 2 (Week 0) and Visit 5 (Week 12).
- Change in mean sitting DBP and SBP between:
 - Visit 2 (Week 0) and Visit 3 (Week 4)
 - Visit 2 (Week 0) and Visit 4 (Week 8)
- Number and proportion of patients achieving the standard BP goal (sitting BP < 140/90 mmHg) at Visit 5 (Week 12).

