## Algorithm for Prior / Concomitant Medications:

START	STOP	ACTION
DATE	DATE	
Known	Known	If stop date < study med start date, assign as prior
		If stop date >= study med start date and start date <= study med
		end date, assign as concomitant
		If stop date >= study med start date and start date > study med
		end date, assign as post study
	Partial	Impute stop date as latest possible date (i.e. last day of month if
		day unknown or 31st December if day and month are
		unknown), then:
		If stop date < study med start date, assign as prior
		If stop date >= study med start date and start date <= study med
		end date, assign as concomitant
		If stop date >= study med start date and start date > study med
		end date, assign as post treatment
	Missing	If stop date is missing could never be assumed a prior
		medication
		If start date <= study med end date, assign as concomitant
		If start date > study med end date, assign as post treatment
		if start date stady fired that date, assign as post treatment
Partial	Known	Impute start date as earliest possible date (i.e. first day of month
Partial	Known	Impute start date as earliest possible date (i.e. first day of month if day unknown or 1st January if day and month are unknown),
Partial	Known	Impute start date as earliest possible date (i.e. first day of month if day unknown or 1st January if day and month are unknown), then:
Partial	Known	Impute start date as earliest possible date (i.e. first day of month if day unknown or 1st January if day and month are unknown), then:  If stop date < study med start date, assign as prior
Partial	Known	Impute start date as earliest possible date (i.e. first day of month if day unknown or 1st January if day and month are unknown), then:  If stop date < study med start date, assign as prior  If stop date >= study med start date and start date <= study med
Partial	Known	Impute start date as earliest possible date (i.e. first day of month if day unknown or 1st January if day and month are unknown), then:  If stop date < study med start date, assign as prior  If stop date >= study med start date and start date <= study med end date, assign as concomitant

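### SAP 13 places concomitant medications by start date only, so drugs carried into the combination period are left out of the Combination Therapy column

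*SAP*

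**What the plan says.** SAP 13 plans the tables: "Frequency tabulations will be presented for prior and concomitant medications by primary therapeutic subgroup" and preferred name, shown for Monotherapy and Combination Therapy in the safety set.

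Two sentences decide the column. One sends earlier starts to the Monotherapy column: "Concomitant medications that are started prior to the first dose of Combination Therapy will be summarized under" that label. The other reserves the Combination Therapy column for later starts: "Concomitant medications that are started after the first dose of Combination Therapy will be summarized under" that label.

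The stop date appears only in the definition that separates concomitant from prior medication; a concomitant record is one that "ended on or after the date of first dose of study medication or were ongoing at the end of the study". The algorithm at the end of the SAP sorts records into prior, concomitant and post treatment against the study medication dates, with lines such as "If start date <= study med end date, assign as concomitant". It has no step that assigns a period.

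The protocol bears on this in three places:

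- Section 12.5: "Prior and concomitant medications will be summarized for combination therapy (NEB + RAM").
- Section 4, secondary safety endpoint: "use of concomitant medications at Visit 2 (Week 0), Visit 3 (Week 4), Visit 4 (Week 8) and Visit 5 (Week 12").
- Section 7.5: where possible, "patients should remain on the same concomitant medication at a stable dose throughout the" study.

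**The concern.** Placing a record by its onset suits events. A medication is an exposure that lasts, and the endpoint asks about its use. The protocol prefers background treatment to stay stable, and note g to the Schedule of Assessments has medications ongoing at consent recorded. The design therefore expects many records that begin before the first combination dose and run on. Those are the records that the two sentences keep out of the Combination Therapy column.

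A reader of the study report would take that column to show what was given alongside nebivolol plus ramipril during the Assessment period. It would show only what was newly started. SAP 3.3, which lists changes from the planned analysis, deals with the two site exclusions and does not mention this.

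**Working it through.** There is no plan figure to reproduce, so the check applies the rule as written to example records. Inputs: Day 1 is the first combination dose and the run-in covers days -28 to -1 (SAP 6.1). I assume the first monotherapy dose falls on day -28. The records are invented to cover the possible patterns.

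Rule as written (SAP 13): a record that both starts and stops before day -28 is prior. Otherwise, start before day 1 gives Monotherapy and start after day 1 gives Combination Therapy.

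Overlap rule: Monotherapy if taken on any day from -28 to -1; Combination Therapy if taken on any day from day 1.

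| Record | SAP 13 as written | Overlap rule |
|---|---|---|
| Day -1825, ongoing | Monotherapy | Both |
| Day -5, ongoing | Monotherapy | Both |
| Day -20 to day -10 | Monotherapy | Monotherapy |
| Day 1, ongoing | Neither, read literally | Combination Therapy |
| Day 30 to day 40 | Combination Therapy | Combination Therapy |
| Day -200 to day -60 | Prior | Prior |

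The first two rows carry the point: both drugs are taken on every day of the 12 weeks and neither reaches the Combination Therapy column. The fourth row is a wording gap only, taken up under the objection. The remaining rows do not change.

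Size, for one drug, leaving Day 1 starts aside. Let N be the patients who took combination therapy, n those with a record begun after the first combination dose, and c those whose use in that period comes only from records begun before it.

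- Planned column: n / N
- Actual use in the period: (n + c) / N
- Shortfall: (n + c) / N - n / N = c / N

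The shortfall runs from zero, when nobody carries the drug over, to the whole of its use, when n = 0. The documents give no rate of long-term use, so c cannot be filled in.

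Against the endpoint: of the four named visits, three (Visits 3, 4 and 5) fall on combination therapy. Use at those visits includes carried-over drugs, and the planned column does not.

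**The case against.** The case for leaving the text alone has several parts.

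- **The rule is disclosed and resembles the one for adverse events** in SAP 18.1. True, but onset is the right basis for an event and the wrong one for continuing use.
- **The Monotherapy sentence does not say that a drug appears there only.** Also true. The Combination Therapy sentence still admits only later starts, and no other text adds carried-over drugs.
- **The protocol does not prescribe an overlap rule, and the endpoint is by visit.** This stands in part. Section 12.5 does not say how to assign a period, and counting by period does not itself give use at each visit. It does make the column report use.
- **Nothing is lost from the database, and the table shells are not available here.** Start and stop dates remain, and a listing or footnote cannot be ruled out. A dose change entered as a new record could also bring a long-term drug into the Combination Therapy column. These points limit the harm but do not correct the stated rule.

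Three stronger readings are tempting, and the documents do not support them.

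1. *Blood-pressure-modifying drugs running at Visit 2 would go unseen.* Protocol 7.6 bars the listed drugs from screening to end of treatment, exclusion criterion 20 covers patients who cannot stop them, and SAP 9.2 has all deviations reviewed and listed before lock. That summary splits by incidence date, so a carried-over drug might sit under Monotherapy there too, but detection does not rest on the medication table.
2. *A drug started on the day of the first combination dose is dropped.* Read alone, SAP 13 covers only starts before or after that dose. SAP 6.2, however, treats medications commencing on the reference start date as post-baseline, and SAP 6.1 makes that date the day of the first combination dose. The wording needs aligning; the record is not without a classification.
3. *Almost all background treatment vanishes, or the efficacy result is distorted.* No usage rate is given, and no blood pressure analysis uses this allocation.

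**Conclusion.** The point holds for the descriptive concomitant-medication tables. As written, SAP 13 makes the Combination Therapy column a count of new starts, and it under-reports concomitant use in that period by c / N for each drug. That falls short of what protocol 12.5 and the secondary safety endpoint ask to have summarised. The primary and secondary blood pressure analyses and the analysis sets are unchanged.

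The conclusion rests on the plain wording of SAP 13 and on the absence of any carry-over rule elsewhere in the SAP. It assumes that the table shells do not override the text. The number of patients affected depends on use that the documents do not report.

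**What to change.** Replace the two allocation sentences in SAP 13 with an overlap rule:

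- Monotherapy, if the medication was taken on any day from the first monotherapy dose to the day before the first combination dose.
- Combination Therapy, if it was taken on any day on or after the first combination dose.
- Flag separately the medications newly started in the combination period, so that the information in the current column is kept.

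Using *on or after* in place of *after* brings SAP 13 into line with SAP 6.2 and with the treatment-emergent rule in SAP 18.1. For a patient who never starts combination therapy, state that the Monotherapy interval ends with monotherapy.

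The cost is two SAP sentences and a changed date condition in one table program, using start and stop dates that the SAP's algorithm already needs. The one drawback is that a medication can count in both columns, so the columns cannot be added together; a footnote should say so.

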## 14. STUDY MEDICATION EXPOSURE

Exposure to study medication for both Monotherapy and Combination therapy in days will be presented for the SAF population.

The date of first study medication administration will be taken from the eCRF "Exposure" form. The date of last study medication will be taken from the eCRF "End of Study Treatment" form. Interruptions, Adherence, and dose changes are not taken into account for duration of exposure.

#### 14.1. Derivations

Duration of exposure (days) = date of last study medication administration – date of first study medication administration + 1.

## 15. STUDY MEDICATION ADHERENCE

Adherence with study treatment will be assessed at Visit 2 for monotherapy and Visit 3, Visit 4, and Visit 5 for the combination therapy and it will be presented for the SAF population. A table consisting of summary statistics for percent Adherence along with the number and percent of patients with Adherence in each of the following groups:

Low: percentage of Adherence <80%

Page 26 of 46

Normal: percentage of Adherence =>80% - <=120%

High: percentage of Adherence >120%

For patients who permanently stop the study medication, the "Date of Visit X(n)" will be replaced by the date of study withdrawal.

Adherence to study medication on SAF population for Monotherapy, and SAF population for Combination Therapy. By visit (Visit 2 for monotherapy and Visit 3, Visit 4 and Visit 5) and overall adherence will be produced for Combination Therapy.

A listing of drug accountability will be presented on SAF populations by phase to account for all drug distributed to each patient, including the box number, total number tablets dispensed, returned, consumed, lost (if any), percentage adherence and compliant (yes/no).

A listing of patient continuing the study (eCRF page: Subject Continuation) will be presented for SAF population for Subject's treatment adherence.

- ranging between 80% to 120%?,
- subject tolerate the treatment?,
- subject present uncontrolled BP
- subject continue to the next visit?.

A patient who has taken at least 80% and no more than 120% of the required study medication intake since the last visit will be considered as adherent.

After 4 weeks  $\pm$  2 days in the Assessment period (Week 4), patients BP will be further evaluated at Visit 3: patients with controlled BP levels (sitting BP < 130/80 mmHg in patients < 65 years old/sitting BP < 140/80 mmHg in patients  $\geq$  65 years old) will continue the same extemporaneous combination, while patients with uncontrolled BP levels (sitting BP  $\geq$  130/80 mmHg in patients < 65 years old/sitting BP  $\geq$  140/80 mmHg in patients  $\geq$  65 years old) will be up-titrated from NEB/RAM 5/2.5 mg to NEB/RAM 5/5 mg for further 4 weeks  $\pm$  2 days.

After further 4 weeks  $\pm$  2 days (Week 8) the BP will be assessed again (Visit 4): controlled patients will continue the same extemporaneous combination, while uncontrolled patients:

- if on NEB/RAM 5/2.5 mg, will be up-titrated to NEB/RAM 5/5 mg for further 4 weeks ± 2 days (Visit 5, Week 12);
- if on NEB/RAM 5/5 mg, will be up-titrated to NEB/RAM 5/10 mg for further 4 weeks  $\pm$  2 days (Visit 5, Week 12).

At the end of the Assessment period (12 weeks  $\pm$  2 days) at Visit 5, the antihypertensive effect of the extemporaneous combination (NEB/RAM 5/2.5 mg, NEB/RAM 5/5 mg or NEB/RAM 5/10 mg) will be evaluated.

Page 27 of 46

#### 15.1. Derivations

Monotherapy and Combination Therapy adherence with study drug based on the drug accountability data will be calculated as the number of doses taken during the study x 100 / number of doses to be taken during the study expressed as a percentage.

For Monotherapy, the expected number of doses to be taken = (Treatment End Date – Treatment Start Date) + 1.

For Combination Therapy, the expected number of doses to be taken = 2 \* ((Treatment End Date - Treatment Start Date) + 1).

For patients who permanently stop the study medication (i.e., monotherapy and/or combination therapy), the expected number of tablets will be calculated up-to the date of study withdrawal.

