Each trial participant is provided with 1 treatment Patient Kit made up by:

- NEB 5 mg: 1 box containing nebivolol 5 mg 42 tablets (3 blisters with 14 tablets).
- RAM 2.5 mg: 1 box containing ramipril 2.5 mg 42 tablets (3 blisters with 14 tablets).

The 2 boxes are then sealed together into a transparent plastic film to realize the treatment patient kit.

Trial participant must be carefully instructed by Investigator or designee to take simultaneously (at the same time): NEB 5 mg as one white round tablet and RAM 2.5 mg as one yellowish oblong tablet, according to Study Protocol.

REVARIN	Global Medical Department		
		Protocol Template	
Identification Number	Version Number	State	Effective date
FORM-000050125	3.0, CURRENT	Effective	13 May, 2022

Visit 3 (Assessment Period):

Participants with controlled BP are provided with 1 treatment Patient Kit made up by:

- NEB 5 mg: 1 box containing nebivolol 5 mg 42 tablets (3 blisters with 14 tablets).
- RAM 2.5 mg: 1 box containing ramipril 2.5 mg 42 tablets (3 blisters with 14 tablets). The 2 boxes are then sealed together into a transparent plastic film to realize the treatment Patient Kit.

Trial participant must be carefully instructed by Investigator or designee to take simultaneously (at the same time): NEB 5 mg as one white round tablet and RAM 2.5 mg as one yellowish oblong tablet, according to Study Protocol.

Participants with uncontrolled BP are provided with 1 treatment patient kit made up by:

- NEB 5 mg: 1 box containing nebivolol 5 mg 42 tablets (3 blisters with 14 tablets).
- RAM 5 mg: 1 box containing ramipril 5 mg 42 tablets (3 blisters with 14 tablets).

The 2 boxes are then sealed together into a transparent plastic film to realize the treatment patient kit.

Trial participant must be carefully instructed by Investigator or designee to take simultaneously (at the same time): NEB 5 mg as one white round tablet and RAM 5 mg as one light red oblong tablet, according to Study Protocol.

Visit 4 (Assessment Period):

Participants with controlled BP who were on NEB/RAM 5/2.5 mg are provided with 1 treatment Patient Kit made up of:

• NEB 5 mg: 1 box containing nebivolol 5 mg 42 tablets (3 blisters with 14 tablets).

• RAM 2.5 mg: 1 box containing ramipril 2.5 mg 42 tablets (3 blisters with 14 tablets). The 2 boxes are then sealed together into a transparent plastic film to realize the treatment patient kit.

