7.4 Study Product Adherence

Adherence with study treatment will be assessed at Visit 2 for monotherapy and Visit 3, Visit 4, and Visit 5 for the combination therapy. The PI must instruct patients to return the medications at each visit. The amount of study medication taken by the patient will be derived by counting the number of tablets in the blister returned and will be recorded in the source document and in the electronic case report form (eCRF).

Adherence to treatment will be estimated by using the below formula:

(number of doses taken during the study)/(number of doses to be taken during the study)×100

A patient who has taken at least 80% and no more than 120% of the required study medication intake since the last visit will be considered as adherent.

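### Combination adherence is a single pooled tablet ratio, so a patient can be classed as adherent while missing about 39% of one of the two drugs

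*SAP*

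**What the plan says.** SAP 15.1 calculates adherence from drug accountability data as doses taken times 100, divided by the "number of doses to be taken during the study expressed as a percentage". For the run-in it says: "For Monotherapy, the expected number of doses to be taken = (Treatment End Date – Treatment Start Date) + 1". For the assessment period it says: "For Combination Therapy, the expected number of doses to be taken = 2" times that same number of days. The section does not say in words that the numerator adds the two drugs, but the factor of 2 implies it, and the same section uses tablets as the unit for patients who stop treatment.

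SAP 15 sorts the result into three categories, the middle one being "Normal: percentage of Adherence =>80% - <=120" percent. It is applied per patient and not per drug. The adherent patient is defined in the same terms in both documents; in Protocol 7.4 it is "A patient who has taken at least 80% and no more than 120% of the required study medication intake since the last visit". Neither document defines a percentage for each drug or requires each drug to reach 80%.

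The two drugs are separate once-daily tablets. Each combination kit holds one box of each drug, for example "NEB 5 mg: 1 box containing nebivolol 5 mg 42 tablets (3 blisters with 14 tablets"), to cover about 28 days. The SAP 15 accountability listing gives details by patient, "including the box number, total number tablets dispensed, returned, consumed, lost (if any), percentage adherence and compliant (yes/no").

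**The concern.** Both drugs have the same expected count, so the pooled percentage is the average of the two per-drug percentages. An average inside 80-120% does not show that each part is inside it. The trial asks what happens when patients uncontrolled on one drug take both, and Protocol Section 4 justifies the adherence endpoint by its value in evaluating the efficacy and tolerability of the combination. A classification that does not separate balanced intake of both drugs from a substantial shortfall in one serves that purpose poorly.

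Ramipril is the titrated component, and SAP 16.2.1.4 and 16.2.1.5 compare patients by ramipril step. A reader of those comparisons would want to know whether ramipril itself was taken, and the planned adherence classification does not answer that.

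**Working it through.** The documents give no numerical adherence result to reproduce, so this applies the SAP 15.1 formula directly.

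**Inputs.** One tablet of each drug per day (Protocol Section 7, Table 1); 42 tablets of each drug per kit (Protocol 7.1); 28 days between visits, with the 2-day window giving 26 to 30; band 80-120% (SAP 15, Protocol 7.4).

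**Formula.** With x and y tablets taken over d days, pooled adherence = (x + y) / (2d) = the mean of x/d and y/d.

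**Limits at 28 days.** Expected 2 × 28 = 56. Lower limit 0.8 × 56 = 44.8, so at least 45 tablets. Upper limit 1.2 × 56 = 67.2, so at most 67.

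| Tablets (one drug + other) | Pooled | Pooled class | Per drug |
|---|---|---|---|
| 28 + 17 | 45/56 = 80.4% | Normal | 100% and 60.7% (39.3% missed) |
| 33 + 12 | 45/56 = 80.4% | Normal | 117.9% and 42.9% (57.1% missed) |
| 42 + 3 | 45/56 = 80.4% | Normal | 150% and 10.7% (89.3% missed) |
| 28 + 39 | 67/56 = 119.6% | Normal | 100% and 139.3% |
| 28 + 0 | 28/56 = 50.0% | Low | 100% and 0% |

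The first row needs no over-use. The second and third need the other drug taken, or counted as taken, above schedule. The fourth shows over-use being masked. The last shows that plain omission of one drug is caught.

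**Visit window.** With one drug exactly as scheduled:
- 26 days: 26 + 16 = 42/52 = 80.8%, 38.5% of the other missed.
- 30 days: 30 + 18 = 48/60 = 80.0%, 40.0% missed.

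**Overall, 84 days.** 84 + 51 = 135/168 = 80.4%, again 39.3% of one drug missed. The overall summary has the same property as the by-visit one.

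**Same band applied to each drug, 28 days.** 0.8 × 28 = 22.4 and 1.2 × 28 = 33.6, so 23 to 33 tablets of each drug (82.1% to 117.9%). All five rows above would then be classed as not adherent to the combination.

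**The case against.** The strongest reply is that the pattern is unlikely, visible elsewhere and of limited consequence.

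- **Likelihood.** The two boxes are wrapped as one kit, and patients are told to take one tablet of each together, told apart by shape and colour (Protocol 7.1). This works against selective intake, and the documents give no frequency of imbalance. That stands, and it limits the likely size of the effect. It does not prevent the 28 + 17 case.
- **Visibility.** Returned tablets of both drugs are checked at each combination visit, accountability discrepancies must be explained (Protocol 7.2), and the SAP listing shows counts, including lost tablets. This helps in part. The SAP does not say whether the box number identifies the drug or the kit, and the summary table and the yes/no classification still rest on the pooled percentage.
- **Consistency with the protocol.** The SAP follows the protocol's single formula and band, so there is no contradiction between the documents. That is correct; the point is that a better measure is available from the same data.

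A reader might infer that a patient effectively on monotherapy would be reported as adherent. The documents do not support this in general: one drug as scheduled and none of the other gives 50%, which is Low. Missing nearly all of one drug goes unseen only if the other is at about 150% of schedule over 28 days.

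**Conclusion.** The point holds in this form. Under SAP 15.1 a patient can be classed as adherent to the combination while missing up to about 39% of one drug over 28 days (40% at 30 days), with the other taken exactly as scheduled. Larger shortfalls pass only with over-use, or apparent over-use, of the other drug. Over-use of one drug to 139% can also pass as Normal.

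The effect is on one secondary endpoint. A reader might infer that the main result or the per-protocol check is compromised, and the documents do not support that. The primary paired test uses the mITT set, which has no adherence criterion. The Visit 2 check concerns monotherapy, where nothing is pooled. Whether adherence removes patients from the per-protocol set depends on the deviation management plan cited in SAP 9.2, which is not among the documents.

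The conclusion assumes that the numerator sums tablets of both drugs, as the factor of 2 implies. How many patients would be reclassified cannot be estimated from the documents.

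**What to change.** In SAP 15.1, derive adherence separately for nebivolol and for ramipril, with expected tablets for each equal to the number of treatment days. Count ramipril as one tablet daily whatever the strength. Report both percentages at Visits 3, 4 and 5 and overall. Class a patient as adherent to the combination only if both percentages lie within the plan's existing 80-120% band, and keep the pooled percentage as a descriptive line. Show the drug name in the accountability listing. This concerns the analysis classification only and alters no treatment or withdrawal rule.

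The cost is a small derivation change and matching table shells, which SAP Section 4 allows only with a SAP amendment, so it should be settled before database lock and noted in SAP 3.3. No new data are needed if tablet returns are recorded by drug, which the visit procedures suggest. The reported adherence rate may be slightly lower.
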